5.1.1.1.2 Study Treatments

The following treatment groups are defined for this study:

- Oxybutynin chloride gel in the Post-Amendment 3 open-label period (titrated dose levels of 0.5, 0.75, and 1.0 g of oxybutynin chloride gel per day)
- Placebo in the Pre-Amendment 3 double-blind period
- Oxybutynin chloride gel in the Pre-Amendment 3 double-blind period (titrated dose levels of 0.5, 0.75, and 1.0 g of oxybutynin chloride gel per day)
- Oxybutynin chloride gel in the Pre-Amendment 3 open-label period (titrated dose levels of 0.5, 0.75, and 1.0 g of oxybutynin chloride gel per day)

5.1.1.1.3 Statistical Methodology

The methodologies defined below apply as specified to individual endpoints defined in this SAP. When indicated, two-sided 95% confidence intervals and two-sided p-values will be presented. Individual endpoint analyses may specify exceptions (additions or deletions) to these general definitions.

Table 5-2 Statistical Methodology

Methodology	Description
Categorical counts	Number of participants in individual categories
	 ○ Participants with ≥ 1 qualifying event counted once per individual category
Categorical	Number and percentage of participants in individual categories
descriptives	\circ Participants with ≥ 1 qualifying event counted once per individual category
	○ N1 = participants with a non-missing baseline value
Shift analysis	 Number and percentage of participants in individual baseline and postbaseline
	categories
	• Percentage denominator = number of participants in individual baseline categories
	• N1 = participants with non-missing values at both baseline and the specified
	postbaseline analysis visit
	• Shifts include: Normal \rightarrow Low, Normal \rightarrow High, High \rightarrow Low, High \rightarrow Normal,
	Low \rightarrow High, Low \rightarrow Normal for continuous variables and Normal \rightarrow Abnormal for
	categorical variables
Continuous	• N1, mean, standard deviation (SD), median, minimum, maximum, 25 th percentile,
descriptives	75 th percentile, standard error of mean (SEM) for a visit in an analysis group
GED 1	N1 = participants with non-missing value for a visit in an analysis group
CFB descriptives	• Continuous descriptives for baseline, postbaseline, and change from baseline (CFB)
	values for an analysis group
	N1 = participants with non-missing values at both baseline and the specified
CED1- 4	postbaseline analysis visit for an analysis group
CFB one-sample t- test	• Estimates derived from one-sample t-test at an analysis visit (observed case [OC] or
test	LOCF, e.g., Week 6 LOCF) for an analysis group o mean and 95% confidence interval (CI)
	o P-value
	N1=participants with non-missing values at both baseline and the specified
	postbaseline analysis visit (in the Post-Amendment 3 ITT and PP populations and in
	the Pre-Amendment 3 and Post-Amendment 3 ITT and PP populations, including
	for each sex, within an age group, or within an weight category within an age
	group)
CFB ANCOVA	Continuous descriptives and standard error (SE) for baseline, postbaseline, and CFB
	values at an analysis visit (e.g., Week 6 LOCF)
	 Estimates derived from a model for CFB value controlling for factors (treatment
	group) and covariates (baseline value)
	Least squares (LS) means and standard errors
	LS mean differences, and 95% confidence intervals for oxybutynin chloride
	gel vs Placebo
	 P-values from contrast t-test comparing oxybutynin chloride gel vs Placebo
	N1 = portioinants with non-missing values at both baseline and the specific 1
	• N1 = participants with non-missing values at both baseline and the specified postbaseline analysis visit
Exact (Clopper-	Exact 95% CI for a single proportion
Pearson) 95% CI	Exact 9370 CI for a single proportion
1 carson, 75/0 Cl	

SAP OG09002 Oxybutynin Chloride 10% Gel

Methodology	Description
Exact	• Exact 95% CI for difference between two proportions
unconditional 95%	
CI using the score	
statistic	
Cochran-Mantel-	P-value from CMH test controlling for baseline covariates
Haenszel (CMH)	
Kolmogorov-	P-value from exact Kolmogorov-Smirnov test to examine whether two distributions
Smirnov test	are the same

CFB = change from baseline; ANCOVA = analysis of covariance.

Raw and derived data listings will be provided, and will be fully defined in the table, figure, and data listing specification document.

5.1.1.1.4 Missing Data

General missing data handling conventions for methodologies in Section 5.1.1.1.3 are summarized as follows:

Table 5-3 Missing Data Handling by Endpoint Type

Parameter type	Timing	Missing Data Handling
CFB ANCOVA	Treatment Period	 If missing a covariate: ○ Participant excluded If missing derived value at the specified post-baseline analysis visit: ○ Available cases (i.e., observed case [OC] analysis) ■ Participant excluded ○ Last observation carried forward (LOCF) ■ Participant included using LOCF-imputed value (last non-missing post-baseline value before the missing value is carried forward to impute the missing value). Baseline value will not be carried forward.

5.1.1.2 Demographics

5.1.1.2.1 Analysis Populations

The distribution of participants within the analysis populations will be summarized as follows:

Table 5-4 Analysis Population Summaries

Population	Description	Methodology	
Combined open-label safety	Distribution by titrated dose level and overall	Categorical counts	
Combined ITT	Distribution by study part and treatment group, oxybutynin chloride gel dose level and all gel dose levels as applicable	Categorical counts	

5.1.1.2.2 Participant Disposition

Participant disposition encompasses the distribution of participants who enter, complete, and discontinue, along with eCRF-reported discontinuation reasons. Participant disposition will be summarized as follows:

Table 5-5 Participant Disposition Summaries

Parameter	Description	Timing	Methodology
Completion and	Summary completion and discontinuation	_	Categorical
discontinuation	status, including summary of reasons for		descriptive
	discontinuation		
ITT population	Distribution in the combined ITT	_	Categorical
summary	population in total and by treatment group;		descriptives
	and by study part in total and by treatment		
	group		

5.1.1.2.3 Protocol Deviations

Protocol deviations will be defined in a separate document, including importance classification. Protocol deviations will be summarized as follows:

Table 5-6 Protocol Deviation Summary

Parameter	Description	Timing	Methodology
Important protocol	Distribution in the combined ITT	_	Categorical
deviations	population in total and by treatment group; and by study part in total and by treatment		descriptives
	group		

5.1.1.2.4 Demographics and Baseline Characteristics

Demographics and baseline characteristics will be summarized as follows:

- Combined ITT population: double-blind period by treatment group and overall and openlabel periods by oxybutynin chloride gel dose level and overall
- Combined open-label safety population: by oxybutynin chloride gel dose level and overall
- Post-Amendment 3 open-label safety population: by oxybutynin chloride gel dose level and overall

The following demographic and baseline characteristics will be summarized as described below:

Table 5-7 Demographic Summaries

Parameter	Description	Timing	Methodology
Age	Age (years) relative to informed consent date	Informed consent	Continuous descriptives
Age group	 3 to < 6 years 6 to < 12 years 12 to <17 years 	Informed consent	Categorical descriptives
Sex, race, and ethnicity	 eCRF categories Race group White Non-white 	Screening Period	Categorical descriptives
Baseline characteristics	 Height (m) Weight (kg) Body mass index (BMI) Weight (kg) / height (m)² 	Latest assessment in Screening Period	Continuous descriptives
Baseline characteristics	 Age and Weight Category <=18 kg and 3 to < 6 years >18 kg and 3 to < 6 years <=25 kg and 6 to < 12 years >25 kg and 6 to < 12 years <=50 kg and 12 to <17 years >50 kg and 12 to <17 years 	Latest assessment in Screening Period	Categorical descriptives

5.1.1.2.5 Medical History

The results of urinary and bowel movement history will be presented for each analysis population as follows:

[figure not shown]
- Combined open-label safety population: by oxybutynin chloride gel dose level and overall
- Post-Amendment 3 open-label safety population: by oxybutynin chloride gel dose level and overall
- Pre-Amendment 3 double-blind safety population: by treatment group and overall

Other medical history will be presented in a listing.

Urinary and bowel movement history reported as occurring before the Screening Visit will be summarized by treatment group or dose level for the safety populations as follows:

Table 5-8 Medical History Summary

Parameter	Description	Timing	Methodology
Urinary and Bowel Movement history	Urinary and Bowel Movement history was present before the Screening Visit	Screening Period	Categorical descriptives

5.1.1.2.6 Prior and Concomitant Medications

Prior medication and concomitant medication use will be summarized separately. The results of prior and concomitant medications will be presented for safety populations as follows:

- Combined open-label safety population: by oxybutynin chloride gel dose level and overall
- Post-Amendment 3 open-label safety population: by oxybutynin chloride gel dose level and overall
- Pre-Amendment 3 double-blind safety population: by treatment group and overall

Medications will be coded using the World Health Organization (WHO) Drug Dictionary, Version WHODRUG DDE + HD 3Q2016 or newer. Unique participants who reported medications will be summarized by Anatomical Therapeutic Chemical (ATC) 4 class and PT in total and for each group or groups defined above for the respective safety population as follows:

Table 5-9 Medication Summaries

Parameter	Description	Timing	Methodology
Prior medications	Medications taken ≥ 1 time before the study treatment start date, regardless of medication end date	Screening Period	Categorical descriptives
Concomitant medications	Medications taken ≥ 1 time on or after the study treatment start date, regardless of medication start date	Treatment Period	Categorical descriptives

ATC4 classes will be sorted alphabetically; PTs will be sorted in descending frequency in the highest dose group.

5.1.1.3 Efficacy and Pharmacodynamic Analyses

Efficacy analyses will be based on each ITT and PP Population. Pharmacodynamic analyses will be based on the ITT Population.

The following efficacy assessments and terms are defined:

Table 5-10 Efficacy and Pharmacodynamic Assessments

Assessment/Term	Description		
Urinary diaries	The following parameters are evaluated:		
	Number of catheterizations per day		
	Volume of urine collected at each (after morning awakening)		
	catheterization		
	Leakage incidents between catheterizations		
Urodynamic Assessment	The following parameters are evaluated:		
	Maximal bladder capacity		
	Detrusor pressures at maximum bladder capacity		
	Maximum amplitude of involuntary detrusor contractions		
	Volume at first involuntary detrusor contraction		
	Presence (versus total absence) of involuntary detrusor contractions at >		
	15 cm H ₂ O		

4 //55	P
Assessment/Term	Description

Baseline assessments for applicable efficacy and pharmacodynamic endpoints defined as follows:

Table 5-11 Efficacy and Pharmacodynamic Endpoint Baseline Definitions

Endpoint	Description	Timing
Parameters in Urinary	The available value at the baseline visit	Visit 1/Visit 2 ¹ for Pre-Amendment
diaries and Urodynamic		3,
Assessment		Visit A/Visit B for Post-Amendment
		3

¹ Visit 1/Visit 2 and Visit A/Visit B are defined in Section 6.2.1.

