11.2 Analysis Populations and Databases

Statistical analysis and data tabulation will be performed using *data from the open-label period for patients enrolled after Amendment 3 and the data from the double-blind and open-label periods for patients enrolled prior to Amendment 3 in* the following patient populations unless specified otherwise:

- Safety populations:
 - Post-Amendment 3 open-label safety population
 - Pre-Amendment 3 double-blind safety population
 - Pre-Amendment 3 open-label safety population
 - Combined open-label safety population (Pre- and Post-Amendment 3)
- Intent-to-treat (ITT) populations:
 - Combined ITT population (Pre- and Post-Amendment 3; primary efficacy analysis population)
 - Post-Amendment 3 ITT population
 - Pre-Amendment 3 ITT population

- Per-protocol (PP) populations:
 - Post-Amendment 3 PP population
 - Pre-Amendment 3 PP population
- PK populations:
 - Post-Amendment 3 PK population
 - Pre-Amendment 3 PK population
 - Combined PK population (Pre- and Post-Amendment 3)

The *Post-Amendment 3 open-label* safety population is defined as all *patients* who receive at least *1* dose of *study treatment in* the open-label period *after Amendment 3*.

The Pre-Amendment 3 double-blind safety population is defined as all patients who receive at least 1 dose of study treatment in the double-blind period before Amendment 3.

The Pre-Amendment 3 open-label safety population is defined as all patients who receive at least 1 dose of study treatment in the open-label period before Amendment 3.

The combined open-label safety population is defined as all patients who receive at least 1 dose of study treatment in the open-label period before or after Amendment 3.

The primary efficacy analysis populations will be the *Post-Amendment 3* ITT population *and the Pre-Amendment 3 ITT population*.

The combined ITT population will include all patients who have a baseline value for the primary efficacy variable in the Post-Amendment 3 open-label period or all randomized patients who have a baseline value for the primary efficacy variable in the Pre-Amendment 3 double-blind period.

The Post-Amendment 3 ITT population will include all randomized patients who have a baseline value for the primary efficacy variable in the Post-Amendment 3 open-label period.

The *Pre-Amendment 3* ITT population will include all randomized patients who have a baseline value for the primary efficacy variable *in the Pre-Amendment 3 double-blind period*.

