11.7.4 Urodynamic Variables

Urodynamic variables will be summarized for the *Pre-Amendment 3 double-blind and Post-Amendment 3* safety populations. *Results will be presented* by treatment group and visit and by treatment group, dose level, and visit for the *Pre-Amendment 3 double-blind* period *and by oxybutynin chloride gel only and visit for the post-Amendment 3 open-label period* using descriptive statistics (mean, 25th percentile, median, 75th percentile, SD, SEM, minimum, maximum, and number of *patients*) for continuous variables and frequency distributions (number and percentage of *patients*) for categorical variables. Summaries will be provided overall and for each age group and *sex*. In addition, descriptive statistics will be presented for change from baseline (baseline is defined as Week 0) for continuous urodynamic variables.

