5.1.1.1 Common Conventions

5.1.1.1.1 Analysis Populations

The analysis populations will consist of participants as defined below, where analysis populations are formed relative to the protocol under which a participant was enrolled. Participants enrolled prior to protocol amendment 3 are referred to as "pre-amendment 3," and participants enrolled under protocol amendment 3 or later are referred to as "post-amendment 3." For example, the pre-amendment 3 safety population consists of all treated participants who received blinded study treatment and may have also received open-label active treatment. The post-amendment 3 safety population consists of all treated participants who received open-label active treatment. Details are below with categorizations based on double-blind or open-label treatment.

[figure not shown]

Table 5-1 Analysis Populations

Population	Definition	Study Treatment
Post-Amendment 3 open- label Safety	All participants who receive at least 1 dose of study treatment in the open-label period who are enrolled under Amendment 3 or	Actual received ¹
Pre-Amendment 3 double-blind Safety	All participants who receive at least 1 dose of study treatment in the double-blind period, which is only applicable to participants who enrolled prior to Amendment 3	Actual received ¹
Pre-Amendment 3 open- label Safety	All participants who receive at least 1 dose of study treatment in the open-label period before Amendment 3	Actual received ¹
Combined open-label Safety (Pre- and Post- Amendment 3)	All participants who receive at least 1 dose of study treatment in the open-label period before or after Amendment 3	Actual received ¹
Post-Amendment 3 Intent-to-Treat (ITT) ²	All participants who receive at least 1 dose of study treatment and have at least one post-baseline value for the primary efficacy variable in the Post-Amendment 3 open-label period	Actual received ¹
Pre-Amendment 3 (Intent-to-Treat) ITT ²	All randomized participants who have at least one post-baseline value for the primary efficacy variable in the Pre-Amendment 3 double-blind period	Randomized assignment

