- average number of catheterizations per day

Analysis populations and methodologies for secondary endpoints will be handled similarly to the primary endpoint. For each secondary endpoint, an exact two-sample Kolmogorov-Smirnov test will be used to compare the two distributions, with a p-value of 0.05 used as the threshold to determine the main analysis method for that endpoint (i.e., the main analysis will use the combined ITT population if $p \ge 0.05$, and the main analysis will analyze the treatment periods separately if p < 0.05).

Efficacy variables will be analyzed as described in the following table. The urinary diary endpoints will be analyzed for the ITT and PP analysis populations at Week 6 (LOCF), and for ITT and PP analysis populations at each OC Visit. The pharmacodynamic endpoints will be analyzed for the ITT population.

Table 5-12 Efficacy and Pharmacodynamic Analyses

Endpoint	Description	Timing	Methodology
Percentage of	Change from baseline to Week 6 (or	Pre-Amendment 3	CFB ANCOVA Pre-
catheterizations without a	LOCF) calculated over 2 diary days	Week 6 (LOCF) of	Amendment 3; CFB
leaking accident		double-blind period;	one-sample t-test
		Post-Amendment 3	Post-Amendment 3;
		Week 6 (LOCF) of	CFB ANCOVA for
		open-label period;	Combined ITT
		Combined ITT	
		(LOCF)	
Percentage of	Raw value for Week 6 (or LOCF)	Pre-Amendment 3	Continuous
catheterizations without a	calculated over 2 diary days	Week 6 (LOCF) of	descriptives
leaking accident		double-blind period;	
		Post-Amendment 3	
		Week 6 (LOCF) of	
		open-label period	
Percentage of	Change from baseline to OC Visits	Pre-Amendment 3	CFB ANCOVA Pre-
catheterizations without a	(Week 2, Week 6) calculated over 2	Week 2, Week 6 of	Amendment 3; CFB
leaking accident	diary days	double-blind period;	one-sample t-test
		Post-Amendment 3	
		Week 6 of open-	

SAP OG09002 Oxybutynin Chloride 10% Gel

Endpoint	Description	Timing	Methodology
		label period; Combined ITT (OC)	Post-Amendment 3; CFB ANCOVA for Combined ITT
Percentage of catheterizations without a leaking accident	Raw value for OC Visits (Week 0, Week 2, Week 6) calculated over 2 diary days	Pre-Amendment 3 Week 0, Week 2, Week 6 of double- blind period; Post-Amendment 3 Week 0, Week 6 of open-label period	Continuous descriptives

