5.1.1.6 Subgroup Analyses

The primary and secondary efficacy LOCF data analyses will be analyzed separately for each group for each ITT population, as appropriate:

Age Group:

- 3 to < 6 years
- 6 to < 12 years
- 12 to < 17 years

Weight Category by Age Group:

- \leq 18 kg and 3 to \leq 6 years
- >18 kg and 3 to < 6 years
- <=25 kg and 6 to < 12 years
- >25 kg and 6 to < 12 years
- <=50 kg and 12 to <17 years
- >50 kg and 12 to <17 years

Sex:

- Male
- Female

Here the same analysis methodologies as the primary and secondary analyses will be applied for the ITT populations (See Section 5.1.1.1.3, CFB ANCOVA). ANCOVA will be performed for each subgroup if the sample size available is at least 14 subjects. The Wilcoxon signed-rank test will be used when the one-sample t-test is not valid (See Section 5.1.1.1.3, CFB one -sample t-test).

Additionally, analysis of other important subgroups may be provided as appropriate.

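### The SAP analyses urodynamics in diary-dependent ITT sets and omits the age-group, sex and dose-level summaries that protocol 11.7.4 specifies, and its change log records neither difference

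*SAP*

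**What the plan says.** **Protocol.** Section 11.7.4 fixes the population: "Urodynamic variables will be summarized for the *Pre-Amendment 3 double-blind and Post-Amendment 3* safety populations". It then asks for results by treatment group and visit, with a further split by dose level for the Pre-Amendment 3 double-blind period.

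The same section adds: "Summaries will be provided overall and for each age group and *sex".

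**SAP, population.** Section 5.1.1.3 says "Pharmacodynamic analyses will be based on the ITT Population", and 5.1.1.3.1 repeats it: "The pharmacodynamic endpoints will be analyzed for the ITT population".

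**SAP, who is in ITT (Table 5-1).** Post-Amendment 3 participants must be treated and "have at least one post-baseline value for the primary efficacy variable in the Post-Amendment 3 open-label period". The Pre-Amendment 3 set is "All randomized participants who have at least one post-baseline value for the primary efficacy variable in the Pre-Amendment 3 double-blind period". The Combined set joins the two. The protocol's own ITT definition (11.2) is looser. For Post-Amendment 3 it "will include all randomized patients who have a baseline value for the primary efficacy variable in the Post-Amendment 3 open-label period", with no post-baseline requirement.

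**SAP, subgroups.** Section 5.1.1.6 opens: "The primary and secondary efficacy LOCF data analyses will be analyzed separately for each group for each ITT population". Urodynamics are neither primary nor secondary efficacy endpoints in the SAP, so this does not reach them. A closing sentence allows other subgroups at discretion. The urodynamic rows of Table 5-12 carry no split by age group, sex or dose level.

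**SAP, change log.** Section 5.2.2 records that urodynamic analysis details and methods for the binary urodynamic variable were added. It does not mention a different population or the absence of the protocol's summaries.

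**The concern.** Pharmacodynamics is part of the secondary objective (protocol 8.2), and protocol 9.6.2.3 bases it on urodynamic testing. Under the SAP, whether a child's bladder pressures and volumes are used depends on a different instrument, the two-day home diary. The diary adds nothing to the validity of a urodynamic measurement. SAP Table 5-2 already limits change analyses to participants with both a baseline and a post-baseline value of the variable analysed. The data at risk come from an invasive test with bladder and rectal catheters (protocol Appendix 4).

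The missing age split matters because Amendment 3 extended enrolment down to age 3, and bladder volumes can be expected to differ between a 3-year-old and a 16-year-old. It also bears on the Combined analysis in Table 5-12. Placebo was given only Pre-Amendment 3, when the minimum age was 6, so children under 6 enter only the active side of that comparison. The ANCOVA has treatment and baseline value but no age term. Age-group summaries would let a reader see how far age mix contributes.

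**Working it through.** The documents give no sample size, power or precision for urodynamics. The only design calculation (93% power, or 90% after 10% dropout) concerns the leakage endpoint and has no bearing here. The check is therefore mainly a comparison of texts.

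**Step 1. Compare the specifications.**

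| Item | Protocol 11.7.4 | SAP |
|---|---|---|
| Population | Pre-Amendment 3 double-blind and Post-Amendment 3 safety | ITT (5.1.1.3, 5.1.1.3.1) |
| Diary needed for entry | No | Yes, post-baseline (Table 5-1) |
| Age group and sex | Yes | Not specified (Table 5-12, 5.1.1.6) |
| Dose level, Pre-Amendment 3 | Yes | Not specified |
| Difference logged | – | No (5.2.2) |

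The omission is not a general simplification: SAP Table 5-22 keeps age group and sex for the anticholinergic questionnaire.

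**Step 2. Identify which children the diary condition can remove.**

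- *Post-Amendment 3.* Urodynamics are done at Visits B and D, and the one post-baseline diary is collected at Visit D (protocol Appendix 1). A child is lost only by attending Visit D for urodynamics with no diary value that can be derived. Protocol 9.5.2.3 does not make the test conditional on the diary. A repeat diary is described only for Visit B (9.5.2.1).
- *Pre-Amendment 3.* Urodynamics are done at Visits 2 and 6, and post-baseline diaries are collected at Week 2 and Week 6 (SAP Appendix 1). One post-baseline value is enough for ITT, so a child is lost only if both diaries are missing.
- *Early leavers.* The final or early-termination visit includes no urodynamics in either part. A child who stops before Week 6 would normally have no paired urodynamic data, and the change analyses would omit that child under either population.

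**Step 3. Illustrate the precision at stake.** Inputs: the planned Post-Amendment 3 minimum of 25 (protocol 11.1), taken for illustration as 25 complete urodynamic pairs; losses of 1 to 5 children are an assumption, since the documents give no rate. The 95% half-width for a mean change, in SD units, is t(0.975, n−1)/√n. The SD cancels in the ratio.

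| n used | Lost | Half-width (SD) | Ratio to n = 25 |
|---|---|---|---|
| 25 | 0 | 0.413 | 1.00 |
| 24 | 1 (4%) | 0.422 | 1.02 |
| 23 | 2 (8%) | 0.432 | 1.05 |
| 20 | 5 (20%) | 0.468 | 1.13 |

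**Step 4. Precision of a separate age-group summary.** The number aged 3 to < 6 is not fixed. By the same formula, the half-width would be about 1.05 SD with 6 children and 0.72 SD with 10 (assumed sizes). Such summaries would be descriptive.

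**The case against.** The case on the other side has several good points.

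- **A reader might infer that children with valid urodynamics are being discarded.** The documents do not show this. They show a rule that can exclude such a child. Step 2 shows that the route is narrow, and protocol Appendix 3 lets site staff review and clarify diary entries when the diary is returned. Neither document sets a completeness threshold for the post-baseline diary. This point stands: the number is unknown and probably small.
- **A reader might infer that children aged 3 to < 6 get no urodynamic result, or that all ages appear only as one mixed mean.** Neither is right. These children count in the Post-Amendment 3 and Combined results. Table 5-12 also reports Pre-Amendment 3 separately, where nobody was under 6. What is missing is a prespecified separate result.
- **A reader might infer a deliberate decision to move or withdraw these analyses.** The last logged SAP version is dated 28 March 2022, and Protocol Amendment 4, dated 31 October 2022, still carries 11.7.4. The SAP describes itself as expanding the protocol's statistical section, and no log entry withdraws the protocol's summaries. This is an unreconciled conflict.
- **The tables may exist elsewhere.** The table specifications are a separate document that was not available, and 5.1.1.6 permits further subgroups. That is possible, but a discretionary clause does not replace a protocol requirement.
- **The root is the SAP's ITT definition.** Under the protocol's baseline-only ITT, and with a correctly completed baseline diary required for entry (IN05), ITT would be close to all enrolled children. That explains the conflict; it does not remove it.

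**Conclusion.** The point holds as a conflict between protocol and SAP on the measure of a secondary objective. The population differs. The SAP's choice makes use of urodynamic data depend on a post-baseline diary. The protocol's summaries by age group, sex and Pre-Amendment 3 dose level are not specified in the SAP, and 5.2.2 records none of this.

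The consequences are limited. A treated child with paired urodynamics can be excluded, but no document says how many would be. The 5% to 13% widening rests on an assumed loss of 2 to 5 from 25 complete pairs, which the plan does not promise; a single loss would cost about 2%. The more certain consequence is that the age group newly admitted by Amendment 3 has no prespecified separate urodynamic result. The primary endpoint is not affected. The change is worth making because the data are already collected.

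**What to change.** In SAP 5.1.1.3, 5.1.1.3.1 and Table 5-12:

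- Base urodynamics on the protocol's Pre-Amendment 3 double-blind and Post-Amendment 3 safety populations, using every participant with a baseline and a post-baseline urodynamic value, whatever the diary status.
- Make Pre-Amendment 3 between-arm comparisons by randomised arm. This must be stated, because the SAP's safety sets are grouped by treatment actually received.
- Restore the descriptive summaries of protocol 11.7.4 by age group (3 to < 6, 6 to < 12, 12 to < 17), by sex, and by dose level for Pre-Amendment 3.
- Record in 5.2.2 any departure from the protocol that is kept, with its reason. If ITT is kept, say which of the three ITT sets applies to which analysis.

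The cost is SAP wording and a few extra tables, with no new data. The drawback is that estimates in small age groups will be imprecise, so they should be presented as descriptive.
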